4.0 BACKGROUND & RATIONALE

4.1 Background

4.1.1 Pharmaceutical and Therapeutic Background

The importance of intact immune surveillance in controlling outgrowth of neoplastic transformation has been known for decades [1]. Accumulating evidence shows a correlation between tumor-infiltrating lymphocytes (TILs) in cancer tissue and favorable prognosis in various malignancies [2; 3; 4; 5; 6]. In particular, the presence of CD8⁺ T-cells and the ratio of CD8⁺ effector T-cells / FoxP3⁺ regulatory T-cells seems to correlate with improved prognosis and long-term survival in many solid tumors.

The PD-1 receptor-ligand interaction is a major pathway hijacked by tumors to suppress immune control. The normal function of PD-1, expressed on the cell surface of activated T-cells under healthy conditions, is to down-modulate unwanted or excessive immune responses, including autoimmune reactions. PD-1 (encoded by the gene *Pdcd1*) is an Ig superfamily member related to CD28 and CTLA-4 which has been shown to negatively regulate antigen receptor signaling upon engagement of its ligands (PD-L1 and/or PD-L2) [7; 8]. The structure of murine PD-1 has been resolved [9]. PD-1 and family members are type I transmembrane glycoproteins containing an Ig Variable-type (V-type) domain responsible for ligand binding and a cytoplasmic tail which is responsible for the binding of signaling molecules. The cytoplasmic tail of PD-1 contains 2 tyrosine-based signaling motifs, an immunoreceptor tyrosine-based inhibition motif (ITIM) and an immunoreceptor tyrosine-based switch motif (ITSM). Following T-cell stimulation, PD-1 recruits the tyrosine phosphatases SHP-1 and SHP-2 to the ITSM motif within its cytoplasmic tail, leading to the dephosphorylation of effector molecules such as CD3 ζ , PKC θ and ZAP70 which are involved in the CD3 T-cell signaling cascade [7; 10; 11; 12]. The mechanism by which PD-1 down modulates T-cell responses is similar to, but distinct from that of CTLA-4 as both molecules regulate an overlapping set of signaling proteins [13; 14]. PD-1 was shown to be expressed on activated lymphocytes including peripheral CD4⁺ and CD8⁺ T-cells, B-cells, T regs and Natural Killer cells [15; 16]. Expression has also been shown during thymic development on CD4-CD8- (double negative) T-cells as well as subsets of macrophages and dendritic cells [17]. The ligands for PD-1 (PD-L1 and PD-L2) are constitutively expressed or can be induced in a variety of cell types, including non-hematopoietic tissues as well as in various tumors [18; 19; 20; 13]. Both ligands are type I transmembrane receptors containing both IgV- and IgC-like domains in the extracellular region and contain short cytoplasmic regions with no known signaling motifs. Binding of either PD-1 ligand to PD-1 inhibits T-cell activation triggered through the T-cell receptor. PD-L1 is expressed at low levels on various non-hematopoietic tissues, most notably on vascular endothelium, whereas PD-L2 protein is only detectably expressed on antigen-presenting cells found in lymphoid tissue or chronic inflammatory environments. PD-L2 is thought to control immune T-cell activation in lymphoid organs, whereas PD-L1 serves to dampen unwarranted T-cell function in peripheral tissues [13]. Although healthy organs express little (if any) PD-L1, a variety of cancers were demonstrated to express abundant levels of this T-cell inhibitor. PD-1 has been suggested to regulate tumor-specific T-cell expansion in subjects with melanoma (MEL) [21]. This suggests that the PD-1/PD-L1 pathway plays a

critical role in tumor immune evasion and should be considered as an attractive target for therapeutic intervention.

MK-3475 (previously known as SCH 900475) is a potent and highly selective humanized monoclonal antibody (mAb) of the IgG4/kappa isotype designed to directly block the interaction between PD-1 and its ligands, PD-L1 and PD-L2.

4.1.2 Preclinical and Clinical Trial Data

Refer to the Investigator's Brochure for Preclinical and Clinical data.

4.2 Rationale

4.2.1 Rationale for the Trial and Selected Subject Population

Radiation has been demonstrated to provide clear survival advantages to patients with both limited stage and extensive stage SCLC^{1,2}. Radiations historical use has been to provide local control, by sterilizing tumor that is non-surgically resectable. Radiations ability to sterilize not only the primary tumor but lymph nodes and draining lymphatic channels have made it an integral part of the treatment of many solid tumors include SCLC which have a proclivity for metastatic spread.

Moreover, despite the known benefit of ionizing radiation in terms of local tumor control, it also enhances the release of cytokines such as TGF- β , a known inducer of tumor invasion and the epithelial-mesenchymal transition.³⁻⁵ On the other hand, radiation can also promote the immune response through the induction of neoantigens and the stimulation of factors such as interferon-gamma that can actually enhance T cell infiltration.⁶ This dual ability to control local tumor progression yet also influence metastatic spread and immune response constitute a compelling argument for including radiation in tests of the current arsenal of immune checkpoint inhibitors now entering the clinic.

The rational for this trial is based on combing MK-3475 with concurrent radiation in order to use radiation ability to turn a tumor into an in situ-vaccine in order to prime an immune response. MK-3475 will provide T cell activation to allowing for priming and expansion of these activated T cells, which can then enter the systemic circulation and enhance systemic tumor control, and concept often referred to as the abscopal affect. Small Cell lung cancer is a disease with a high failure rate both locally and distantly. As such improvement in both systemic and local therapy are urgently needed. Furthermore Small Cell Lung Cancer has one of the highest endogenous mutation rates of any cancer with up to 7 mutations per 1 million bases⁷, all these unique mutations can potentially be used as new antigen for immune stimulation. All this contributes to SCLC being ideal tumor type to evaluate checkpoint inhibitors such as MK-3475.

4.2.2 Rationale for Dose Selection/Regimen/Modification

Radiation for limited stage disease will be administered at the standard doses of 45Gy in twice daily fractions, with concurrent chemotherapy, either cisplatin and etoposide or carboplatin and etoposide. Patients with extensive stage disease will receive thoracic radiation to 45 Gy in daily fractions, without concurrent chemotherapy. While on study, patients are allowed to have further radiation to other clinically appropriate sites as per the discretion of their treating radiation oncologist.

MK-3475: Will be started at 100 mg, 1/2 the MTD of MK-3475 alone (based on MTD dose of 200mg Q 3 weeks). The dose will be changed as per our 3x3 dose escalation rules and either decreased to 70mg, continued at 100m or increased to 150mg and eventually 200mg.

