2.2 Trial Diagram

- For Part A we will allow induction chemotherapy
- Primary Endpoint
 - Safety
- Secondary endpoint
 - Improvement in PFS compared to historical controls

[figure not shown]
Part A: Is only for patients with Limited Stage SCLC, we will allow induction chemotherapy. The total cycles of chemotherapy recommended will be 4, as such if a patient had two cycles of induction chemotherapy they would only get an additional two with MK-3475. PCI will be allowed based on the treating physician discretion and will be done after chemotherapy has been completed. PCI will delay the next dose of MK-3475 by one cycle and PCI should start approximately three weeks after MK-3475. MK-3475 can be resumed following the completion of PCI. LS-SCLC patients, who achieve systemic disease control during/after completion of 16 cycles of MK-3475, will be eligible to get additional 16 cycles of MK-3475, provided they did not exhibit severe (grade >3) MK-3475 related toxicity during therapy. Systemic disease control is defined as stable disease or partial response or complete response, based on irRC criteria.

Part A for LS-SCLC

* Eligible patients may receive additional 16 cycles.

Part B: Is only for patients with Extensive Stage SCLC who are receiving consolidation XRT after 1-6 cycles of chemotherapy. Patients needing PCI are encouraged to have it completed prior to enrollment in this trial. If PCI needs to be given on study, after thoracic XRT, then it should be done in a manner consistent with part A. PCI will delay the next dose of MK-3475 by one cycle and PCI should start approximately three weeks after MK-3475. MK-3475 can be resumed following the completion of PCI.) Patients needing XRT treatment to other sites outside the thorax will be allowed, but is encouraged to be done prior to starting the trial.

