7.1.2.5 Tumor Imaging and Assessment of Disease

Response and progression will be evaluated in this study using guidelines proposed by the Immune Related Response Criteria (irRC). Patients with measurable disease will also be assessed using standard RECIST v 1.1 and World Health Organization (WHO) treatment response criteria.

7.1.2.5.1 irRC: Measurable Disease Prior to Therapy

Index lesions: Up to 15 index lesions per patient (5 per organ, up to 10 visceral and 5 cutaneous) with minimum size 5 x 5 mm will be accurately measured in two dimensions (two largest perpendicular diameters) on CT or MRI scan (slice thickness no greater than 5 mm) prior to therapy initiation. Lesions measured with calipers by clinical exam may be conducted on lesions no smaller than 10 mm in the smallest dimension. Lesions that cannot be accurately measured with calipers should be recorded as non-measurable.

XRT-treated index lesions: Defined as all index lesions treated by XRT as part of this protocol.

Non-XRT-treated index lesions: Defined as all index lesions not treated by XRT as part of this protocol.

irRC: Index and non-Index Lesions:

For the irRC, index and measurable new lesions are taken into account (in contrast to conventional WHO treatment response criteria, which do not require the measurement of new lesions, nor are new lesion measurements included in the assessment of evolving tumor

burden). At the baseline tumor assessment, the sum of the products of the two largest perpendicular diameters (SPD) of all index lesions (five lesions per organ, up to 10 visceral lesions and five cutaneous index lesions) is calculated. At each subsequent tumor assessment, the SPD of the index lesions and of new, measurable lesions ($\geq 5 \times 5$ mm; up to 5 new lesions per organ: 5 new cutaneous lesions and 10 new visceral lesions) are added together to provide the total tumor burden. In addition to a global irRC which will encompass all lesions under the previous definition, the irRC of lesions included within the XRT PTV and outside the XRT PTV will also be assessed as follows:

1. **Global irRC:** irRC that factors all lesions including both index and non-index as outlined in 9.2.4.
2. **In-Field irRC:** irRC in which only index within the XRT PTV will be considered and any non-index lesions arising inside the XRT PTV
3. **Out-Field irRC:** irRC in which only index lesions outside the XRT PTV will be considered and any non-index lesions arising outside the XRT PTV

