Response in new patients will be conducted using the Immune Related Response Criteria (irRC) as described in¹⁰. “For irRC, only index and measurable new lesions are taken into account. At the baseline tumor assessment, the sum of the products of the two largest perpendicular diameters (SPD) of all index lesions (five lesions per organ, up to 10 visceral lesions and five cutaneous index lesions) is calculated. At each subsequent tumor assessment, the SPD of the index lesions and of new, measurable lesions ($\geq 5 \times 5$ mm; up to 5 new lesions per organ: 5 new cutaneous lesions and 10 visceral lesions) are added together to provide the total tumor burden:”

For the purposes of this study, 3 separate tumor burdens will be calculated for each patient and used to define 3 separate irRCs as discussed in 9.3. All criteria will be considered separately for all 3 irRCs: global, in-field, and out-field.

Global Tumor Burden = SPD(all index lesions) + SPD(new, measurable lesions)

In-Field Tumor Burden = SPD(all index lesions targeted by XRT in this protocol) + SPD(new, measurable lesions inside the XRT PTV)

Out-Field Tumor Burden = SPD(all index lesions NOT targeted by XRT in this protocol) + SPD(new, measurable lesions outside the XRT PTV)

Complete Response (irCR): irCR, complete disappearance of all lesions (whether measurable or not, and no new lesions) confirmation by a repeat, consecutive assessment no less than 4 wk from the date first documented.

Partial Response (irPR): irPR, decrease in tumor burden $\geq 50\%$ relative to baseline confirmed by a consecutive assessment at least 4 wk after first documentation.

Progressive Disease (irPD): irPD, increase in tumor burden $\geq 25\%$ relative to nadir (minimum recorded tumor burden) confirmation by a repeat, consecutive assessment no less than 4 wk from the date first documented.

1. If a patient is classified as having irPD at a post-baseline tumor assessment, then confirmation of irPD by a second scan in the absence of rapid clinical deterioration is required. The definition of confirmation of progression represents an increase in tumor burden $\geq 25\%$ compared with the nadir at two consecutive time points at least 4 wk apart. It is recommended that this be done at the discretion of the investigator

because follow-up with observation alone may not be appropriate for patients with a rapid decline in performance status.

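### Permitted radiation between the first and the confirmatory scan can delay, or less often remove, an irRC progression event, and the plan has no rule for it

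*Combined protocol and SAP*

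**What the plan says.** **Radiation.** Section 4.2.2, covering both parts, reads: "While on study, patients are allowed to have further radiation to other clinically appropriate sites as per the discretion of their treating radiation oncologist". For Part B, Section 2.2 adds: "Patients needing XRT treatment to other sites outside the thorax will be allowed, but is encouraged to be done prior to starting the trial". Neither limits the timing or the lesions that may be treated, and the prohibited list in Section 5.4.2 does not name radiation.

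**Progression.** Section 7.1.2.5 makes irRC the system for response and progression, and adds: "Patients with measurable disease will also be assessed using standard RECIST v 1.1 and World Health Organization (WHO) treatment response criteria". Section 7.1.2.5.3 defines confirmed irPD as a rise of at least 25% "compared with the nadir at two consecutive time points at least 4 wk apart", and states that "confirmation of irPD by a second scan in the absence of rapid clinical deterioration is required". A patient who meets none of irCR, irPR or irPD is irSD, with no repeat scan needed. Routine imaging is about every 12 weeks, plus or minus 4 (Section 6.1, footnote e).

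**Burden.** Global burden sums all index lesions and new measurable lesions. In-field and out-field burdens split lesions by whether they were targeted by radiation in this protocol.

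**Analysis.** Section 9.2.4 lists the three irRC versions for efficacy, estimates PFS by Kaplan-Meier, and says that the sample is too small for a formal comparison with historical controls. It defines no PFS event or censoring rule.

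**Part A extension.** Section 2.2 makes a further 16 cycles depend on systemic disease control: "Systemic disease control is defined as stable disease or partial response or complete response, based on irRC criteria".

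**The concern.** The confirmation rule assumes that what happens between the two scans is the natural course of disease under study treatment. Local radiation breaks that assumption. A lesion that grew, was irradiated and then shrank looks on the second scan as if the first reading had been a false alarm. Nothing in Sections 7.1.2.5.3 or 9.2.4 excludes, flags or otherwise handles such a lesion.

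The error has a direction. Radiation to a growing lesion is given to patients who appear to be progressing, so the events delayed or lost come from them and PFS looks longer. Improvement in PFS over historical controls is the secondary objective (Section 3.2), so even an informal reading against outside data is affected. The out-field readout may be affected too: the rationale in Section 4.2.1 is a systemic effect of local radiation, and direct shrinkage from discretionary radiation could be scored as out-field response if that radiation is not counted as protocol radiation.

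**Working it through.** The plan states no PFS assumption, event count or power, so there is no figure to reproduce. The check has three steps.

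**1. Can the rule misclassify?** Take a nadir burden of 10 cm², with one lesion growing from 2 to 5 cm² and the rest unchanged.
- First scan: 10 − 2 + 5 = 13, and 13/10 = +30%, which meets the 25% threshold.
- The lesion is irradiated and measures 3 cm² at the second scan: 10 − 2 + 3 = 11, and 11/10 = +10%. irPD is not confirmed and the patient is irSD.
- The threshold is 12.5, so any lesion size below 4.5 cm² defeats confirmation: (5 − 4.5)/5 = 10% shrinkage.
- The nadir stays at 10, so a further 1.5 cm² anywhere brings burden back to the threshold. That is delay, not permanent loss.

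**2. How much shrinkage is needed?** Set nadir to 100. A lesion of size b at nadir brings the total to T at the first scan, so it measures g = b + (T − 100). With all else unchanged, confirmation fails if the lesion loses more than (T − 125)/g.

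| First-scan total T | Lesion was 20 at nadir | Wholly new lesion |
|---|---|---|
| 130 | 5/50 = 10% | 5/30 = 17% |
| 140 | 15/60 = 25% | 15/40 = 38% |
| 150 | 25/70 = 36% | 25/50 = 50% |
| 200 | 75/120 = 62.5% | 75/100 = 75% |

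Modest rises are easily undone and large ones are not. Growth in any other lesion raises the requirement.

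**3. What could it do to PFS?** These inputs are assumptions, not in the documents: exponential progression times with a 6-month median; scans every 12 weeks (12/4.345 = 2.76 months); a share f of first progressions irradiated and left unconfirmed, each replaced by a fresh progression time starting at that scan.

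The chance of passing one scan interval is r = 0.5^(2.76/6) = 0.727. Two scans fall within 6 months and four within 12.
- 6 months: S = (1 − f)·r² + f·[1 − (1 − r)²] = (1 − f)·0.528 + f·0.925
- 12 months: S = (1 − f)·r⁴ + f·[r⁴ + 4(1 − r)r³] = (1 − f)·0.279 + f·0.699

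| f | 6-month PFS | 12-month PFS |
|---|---|---|
| 0 | 52.8% | 27.9% |
| 0.1 | 56.8% | 32.1% |
| 0.2 | 60.8% | 36.3% |
| 0.3 | 64.7% | 40.5% |

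The same 6-month formula for f from 0.1 to 0.3 gives 43% to 53% against 38% with a 4-month median, and 75% to 80% against 73% with a 12-month median. If all 40 patients in one part progressed, f = 0.1 is 4 events and f = 0.2 is 8.

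**The case against.** The strongest reply is that the root defect is the missing PFS definition. RECIST 1.1 and WHO are also assessed, Section 13.3 says RECIST 1.1 will be used for tumor response, and no section assigns a criterion to PFS, so nobody can say that the PFS event is lost. This stands in part. The loss occurs under irRC, which is the main system in Section 7.1.2.5 and the only one listed in Section 9.2.4, but the choice for PFS is not stated. Naming a criterion is therefore part of the fix. If irRC is named, the gap remains.

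A reader might go further and infer that irradiating a growing lesion erases the event and keeps the patient on MK-3475 in disease control. The documents do not support that:
- The second scan is not required when there is rapid clinical deterioration.
- Other lesions may hold burden at or above 125% of nadir, and later growth can still count.
- Section 5.8 lists many reasons to stop besides confirmed progression, and allows some patients with confirmed progression to continue. Continued treatment is therefore not specific to a failed confirmation.
- Section 7.1.4.4.1 moves patients who start a new anti-cancer therapy to survival follow-up. Whether permitted radiation counts is not said there or in Section 7.1.1.4.3.
- The 16-cycle extension applies to Part A only, whereas the separate wording on sites outside the thorax is in Part B.

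It is also fair that the in-field and out-field split was meant to separate irradiated from non-irradiated lesions. It would help if the plan said where later discretionary radiation falls; it does not.

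**Conclusion.** The gap is real and should be closed. Under irRC as written, permitted radiation to a lesion driving a first-scan rise can leave irPD unconfirmed and the patient scored irSD, which delays the PFS event or, less often, removes it. The consequence is upward bias in a descriptive Kaplan-Meier estimate of a secondary endpoint and in its informal reading against historical controls. The primary safety endpoint is untouched, and no test, error rate or power calculation is involved.

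The size is unknown, because the documents give neither a rate of such radiation nor an expected PFS. The rise of about 4 to 8 percentage points in 6-month PFS rests on an assumed 6-month median, an assumed 10% to 20% of first progressions affected, and no other lesion confirming progression. It shows scale and is not a prediction.

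For the Part A extension, the radiation permission (Sections 2.2 and 4.2.2), the confirmation rule (7.1.2.5.3) and the definition of systemic disease control (2.2) need to be reconciled. No clinical rule is proposed here.

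**What to change.** Change Sections 9.2.4 and 7.1.2.5.3 and leave the radiation permission as it is.

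1. Name the criterion (irRC, RECIST 1.1 or WHO) that drives PFS. State whether permitted radiation counts as new anti-cancer therapy, and whether lesions so treated are in-field or out-field.
2. If a first scan calls for confirmation, and a new lesion or a lesion contributing to the rise of at least 25% is irradiated before the confirmatory scan, date progression for the PFS analysis at the first scan. Report PFS under the current confirmation rule as a sensitivity analysis.
3. Give no response credit, in global or out-field irRC, for shrinkage of a lesion irradiated outside the planned thoracic field, but let later regrowth above its pre-radiation size count toward irPD. Entering the larger of the current and the last pre-radiation measurement does both. Simply freezing the pre-radiation value would hide regrowth and bias PFS upward again.
4. Record the date and site of all on-study radiation. The flow chart in Section 6.1 has no item for it.

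**Cost.** One added data field and some wording. PFS becomes slightly less favorable, and an occasional pseudoprogression will be counted as an event; the sensitivity analysis shows how much that matters. Patient care does not change.

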4.2.3 Rationale for Endpoints

4.2.3.1 Efficacy Endpoints

Part A LS-SCLC: The primary endpoint is safety in order to establish the MTD of MK-3475 with concurrent chemo and radiation. The primary acute toxicity for chemo and radiation is esophagitis with a rate of $\geq 32\%$ ⁸. While the long term toxicity rate of grade 3 pneumonitis is around 13%⁹.

Part B ES-SCLC: The primary endpoint is safety in order to establish the MTD of MK-3475 with concurrent radiation. The primary acute toxicity for chemo and radiation is esophagitis with a rate of $\geq 32\%$ ⁸. While the long term toxicity rate of grade 3 pneumonitis is around 13%⁹.

5.0 METHODOLOGY

5.1 Entry Criteria

5.1.1 Diagnosis/Condition for Entry into the Trial

5.1.2 Subject Inclusion Criteria

In order to be eligible for participation in this trial, the subject must:

1. Be willing and able to provide written informed consent/assent for the trial.
2. Be ≥ 18 years of age on day of signing informed consent.
3. Modified for clarification as some patient with induction therapy could have no measurable disease. Have a performance status of 0 or 1 or 2 on the ECOG Performance Scale.
4. Demonstrate adequate organ function as defined below; all screening labs should be performed within 10 days of treatment initiation.

Table 1 Adequate Organ Function Laboratory Values

System	Laboratory Value
Hematological	
Absolute neutrophil count (ANC)	≥1,500 /mcL
Platelets	≥100,000 / mcL
Hemoglobin	≥9 g/dL or ≥5.6 mmol/L
Renal	
Serum creatinine OR Measured or calculated ^a creatinine clearance (GFR can also be used in place of creatinine or CrCl)	≤1.5 X upper limit of normal (ULN) OR ≥60 mL/min for subject with creatinine levels > 1.5 X institutional ULN
Hepatic	
Serum total bilirubin	≤ 1.5 X ULN OR Direct bilirubin ≤ ULN for subjects with total bilirubin levels > 1.5 ULN
AST (SGOT) and ALT (SGPT)	≤ 2.5 X ULN OR ≤ 5 X ULN for subjects with liver metastases
Coagulation	
International Normalized Ratio (INR) or Prothrombin Time (PT)	≤1.5 X ULN unless subject is receiving anticoagulant therapy as long as PT or PTT is within therapeutic range of intended use of anticoagulants
Activated Partial Thromboplastin Time (aPTT)	≤1.5 X ULN unless subject is receiving anticoagulant therapy as long as PT or PTT is within therapeutic range of intended use of anticoagulants
^a Creatinine clearance should be calculated per institutional standard.	

5. Female subject of childbearing potential should have a negative urine or serum pregnancy within 2 weeks of study entry. If the urine test is positive or cannot be confirmed as negative, a serum pregnancy test will be required.
6. Female subjects of childbearing potential should be willing to use 2 methods of birth control or be surgically sterile, or abstain from heterosexual activity for the course of the study through 120 days after the last dose of study medication (Reference Section 5.7.2). Subjects of childbearing potential are those who have not been surgically sterilized or have not been free from menses for > 1 year.
7. Male subjects should agree to use an adequate method of contraception starting with the first dose of study therapy through 120 days after the last dose of study therapy.
8. Histologic diagnosis of either limited state SCLC (LS-SCLC), or Extensive stage SCLC (ES-SCLC) or neuroendocrine tumor.

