3.0 OBJECTIVE(S) & HYPOTHESIS(ES)

3.1 Primary Objective(s) & Hypothesis(es)

- (1) **Objective:** Safety of MK 3475 plus chemo/radiation for LS-SCLC and safety of MK 3475 plus radiation for ES-SCLC

Hypothesis: MK-3475 with chemoradiation for LS-SCLC and with radiation for ES-SCLC will demonstrate an acceptable toxicity profile comparable to previous trials

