8.0 CHEMOTHERAPY

Part A LS-SCLC:

All patients will receive chemotherapy with either cisplatin and etoposide or carboplatin and etoposide. All patients should receive four cycles of chemotherapy, given over 3 weeks each, unless there is evidence of disease progression or patient intolerance. Cisplatin and etoposide is the preferred regimen; for patients unable to tolerate cisplatin in the opinion of the treating clinician, carboplatin/etoposide is an acceptable alternative.

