8.3 Dose Delays and Dose Modifications for Cytotoxic Chemotherapy

8.3.1 Dose Delays

Drug related toxicities must be resolved to baseline or \leq grade 1 (with the exception of alopecia and grade 2 fatigue) prior to administering the next dose. Subjects should not receive the next cycle of chemotherapy if any of the following apply:

- Absolute neutrophil count (ANC) $< 1500/\text{mm}^3$
- Platelet count $< 100,000/\text{mm}^3$
- Hemoglobin $< 9 \text{ g/dL}$
- Total bilirubin > 2.5 times the upper limit of normal (ULN)
- AST and ALT > 2.5 times ULN, or > 5 times ULN if liver metastases are present
- Inadequate renal function defined as creatinine clearance $< 45 \text{ mL/min}$ by the standard Cockcroft and Gault formula
- Additionally, treatment may be delayed due to any other reasons as per the treating physician's discretion.

Chemotherapy treatment may be delayed up to 21 days.

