All patients who receive any MK-3475 will be considered evaluable for response and will be included in the efficacy data set.

DLT is defined as any:

- DLTs are defined as any adverse event(s) considered related to the combination of MK-3475 plus radiation as described below:
 - Any \geq Grade 3 bronchospasm or other hypersensitivity reaction;
 - Any other \geq Grade 3 non-skin related adverse event with the exception of laboratory abnormalities;
 - Any Grade 4 laboratory abnormalities, except AST, ALT, or total bilirubin;
 - AST or ALT $> 8 \times$ ULN,
 - Total bilirubin $> 5 \times$ ULN;
 - Any other Grade 4 adverse event;
- 1. Any adverse event, laboratory abnormality or intercurrent illness which, in the judgment of the investigator, presents a substantial clinical risk to the subject with continued study drug dosing;
- 2. Subject experiences an allergic/infusion reaction while receiving study drug at a slower infusion rate due to a prior allergic/infusion reaction;
- 3. Any motor neurologic toxicity \geq Grade 3 regardless of causality;
- 4. Any \geq Grade 3 treatment-related sensory neurologic toxicity.
- 5. Drug related toxicity that prevents administration of MK-3475 for > 21 days from the scheduled dose
 - The time frame for DLT assessment will be within 22 days of therapy initiation.
 - Any grade 4 neutropenia (with or without fever and/or sepsis) or thrombocytopenia (with or without bleeding) lasting at least 1 week or longer (as defined by the NCI-CTC v4.0).
 - Any other grade 3 non-hematologic toxicity including symptoms/signs of vascular leak or cytokine release syndrome; or any severe or life-threatening complication or abnormality not defined in the NCI-CTCAE v4.0 that is attributable to the therapy.

9.2.1. *Statistical Analysis*

Descriptive statistics will be computed for all relevant outcomes, including toxicity, tumor response, PFS, OS, and biomarker response. Descriptive analysis will include a global assessment of patient outcomes for parts A and B separately. All patients receiving at least 1 treatment with MK-3475 will be included in the analysis.

9.2.2. *Demographics and Baseline Characteristics*

Frequency distributions of gender and race will be tabulated by dose/cohort. Summary statistics for age, body weight, height, and Body Mass Index (BMI) will be tabulated by dose/cohort.

9.2.3. *Safety Analyses*

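### Part A entry sets no creatinine-clearance floor when serum creatinine is at or below 1.5 × ULN, so a patient can qualify with a clearance at which section 8.3.1 holds platinum/etoposide

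*Combined protocol and SAP*

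**What the plan says.** The renal row of Table 1 in section 5.1.2 applies to both parts and offers two routes. Creatinine at or below 1.5 × ULN is enough by itself. Otherwise the patient needs a clearance of "≥60 mL/min for subject with creatinine levels > 1.5 X institutional ULN". GFR may be substituted, but need not be. The footnote leaves the method open: "Creatinine clearance should be calculated per institutional standard". There is no upper age limit.

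In Part A, section 8.0 states: "All patients will receive chemotherapy with either cisplatin and etoposide or carboplatin and etoposide". Section 8.3.1 then sets the hold rule: "Subjects should not receive the next cycle of chemotherapy if any of the following apply". One listed condition is clearance below 45 mL/min "by the standard Cockcroft and Gault formula", which that section labels inadequate renal function. On timing it says: "Chemotherapy treatment may be delayed up to 21 days".

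The primary objective (section 3.1) is "Safety of MK 3475 plus chemo/radiation for LS-SCLC and safety of MK 3475 plus radiation for ES-SCLC". The analysis population (section 9.2.1) is broad: "All patients receiving at least 1 treatment with MK-3475 will be included in the analysis".

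**The concern.** The entry rule and the hold rule use different measures. Entry can rest on serum creatinine alone, whereas the hold uses Cockcroft-Gault clearance, which also depends on age, weight and sex. In an older, lighter or female patient, a creatinine that passes entry can correspond to a clearance well under the hold level. If that clearance is stable, a delay of up to 21 days would not be expected to correct it.

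The text therefore permits enrolment in Part A of a patient whose later cycles section 8.3.1 would withhold. That patient would still count in the Part A safety estimate, which is meant to describe MK-3475 with chemotherapy and radiation, while contributing data nearer to MK-3475 with radiation. Escalation cohorts have 3 or 6 patients, so one such patient is a third or a sixth of a cohort.

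The mismatch looks unintended. The entry limits for neutrophils (1,500), platelets (100,000), hemoglobin (9 g/dL) and AST/ALT (2.5 × ULN, or 5 × with liver metastases) coincide with the hold limits in 8.3.1. The renal limits differ in measure, formula and threshold. The ordering is also odd: a patient just above 1.5 × ULN with a clearance of 59 mL/min is ineligible, while one at 1.5 × ULN with a clearance below 30 is eligible.

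**Working it through.** The plan gives no figure of its own to reproduce. The check applies the protocol's clearance formula to patients who pass Table 1.

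**Inputs**
- Formula (section 8.2.3): clearance = (140 − age) × weight in kg ÷ (72 × creatinine in mg/dL), multiplied by 0.85 for women.
- Hold level (section 8.3.1): below 45 mL/min.
- Entry limit (Table 1): creatinine at or below 1.5 × ULN.
- Assumed, because the documents give no value: ULN of 1.0, 1.1 or 1.2 mg/dL, so an entry limit of 1.5, 1.65 or 1.8 mg/dL.
- Ages and weights are illustrative.

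**Step 1: creatinine at which clearance equals 45.** Rearranged, creatinine = (140 − age) × weight × (0.85 if female) ÷ (72 × 45), and 72 × 45 = 3,240.
- Woman 75 y, 55 kg: 65 × 55 × 0.85 ÷ 3,240 = 0.94 mg/dL
- Woman 70 y, 60 kg: 70 × 60 × 0.85 ÷ 3,240 = 1.10 mg/dL
- Man 70 y, 70 kg: 70 × 70 ÷ 3,240 = 1.51 mg/dL
- Man 55 y, 80 kg: 85 × 80 ÷ 3,240 = 2.10 mg/dL

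**Step 2: clearance at the entry limit (mL/min).**

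| Profile | ULN 1.0 | ULN 1.1 | ULN 1.2 |
|---|---|---|---|
| Woman 75 y, 55 kg | 28.1 | 25.6 | 23.4 |
| Woman 70 y, 60 kg | 33.1 | 30.1 | 27.5 |
| Man 70 y, 70 kg | 45.4 | 41.2 | 37.8 |
| Man 55 y, 80 kg | 63.0 | 57.2 | 52.5 |

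**Step 3: creatinine values that pass entry with clearance below 45.**
- First woman: from just above 0.94 up to 1.5–1.8 mg/dL.
- Second woman: from just above 1.10 up to 1.5–1.8 mg/dL.
- 70-year-old man: none at ULN 1.0; from just above 1.51 up to 1.65–1.8 mg/dL at ULN 1.1–1.2.
- 55-year-old man: none.

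The gap is not confined to the entry limit. The first woman at a creatinine of 1.0 mg/dL has 65 × 55 × 0.85 ÷ 72 = 42.2 mL/min.

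**Step 4: wider range of ULN (0.9 to 1.4).** At 1.5 × ULN, a 65-year-old, 60 kg woman runs from 39.4 down to 25.3 mL/min and is below 45 throughout. A 65-year-old, 70 kg man runs from 54.0 to 34.7, with 48.6 at ULN 1.0 and 44.2 at ULN 1.1.

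**Step 5: is there another numeric barrier at entry?** None was found. Exclusion 10 rests on investigator opinion. Exclusion 4 covers unresolved toxicity from earlier agents but not pre-existing renal disease. Section 8.2.3 requires a calculated clearance before each carboplatin dose, while section 8.2.2, on the preferred agent cisplatin, states no clearance requirement.

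**The case against.** The strongest reply concerns consequence. Section 8.3.1 speaks of the next cycle and does not name the first on-study cycle. It also does not restrict MK-3475 or radiation. DLTs are assessed within 22 days of starting therapy, chemotherapy cycles last 3 weeks, and limited-stage radiation runs over 15 days. An affected patient could receive a full first cycle and meet the hold only around day 22, so escalation decisions would still rest mostly on combined exposure. This largely stands. The main effect would then fall on later descriptive toxicity tables. Two qualifications apply. If 8.3.1 does not govern the first cycle, a low-clearance patient may receive cisplatin at 80 mg/m² with no stated renal limit. And for a patient who has had induction chemotherapy, the first on-study cycle could be read as the next cycle, though the text does not say so.

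It is also fair to say that chemotherapy exposure in Part A already varies by design. Induction cycles count toward the recommended four, intolerance and physician discretion are allowed for, and including everyone with one MK-3475 dose is an ordinary safety population. That makes the added heterogeneity less important, but it does not explain admitting patients whose remaining cycles the protocol would withhold from the outset.

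Finally, frequency is unknown, and an entry floor equal to the hold level only narrows the gap, since a patient entering at 46 mL/min may drop below 45 after one platinum cycle. Both points are correct. They bear on the size of the problem, not on whether it exists.

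**Conclusion.** The concern holds. Table 1 can admit a Part A patient whose Cockcroft-Gault clearance is below the level at which section 8.3.1 holds chemotherapy, and no other criterion sets a numeric floor.

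The profiles affected are ordinary ones, chiefly older or lighter patients and women. Heavier or younger men are mostly spared; a 65-year-old, 80 kg man at 1.5 × ULN with ULN 1.2 is still at 46.3 mL/min. These results rest on the assumed ULN and the illustrative profiles.

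The number of patients affected cannot be estimated from the documents. If 1%, 5% or 10% of Part A were affected (pure assumptions), that would be 0.4, 2 or 4 of 40. The likely harm is dilution of the chemoradiation safety estimate, with limited bearing on the DLT decisions. The change is worth making because it is cheap and removes an internal inconsistency.

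**What to change.** Add one row to Table 1, for Part A only: calculated Cockcroft-Gault clearance of at least 45 mL/min at screening for every patient regardless of serum creatinine, using the formula in section 8.2.3 in place of the institutional method in the footnote. Keep the existing 60 mL/min requirement for creatinine above 1.5 × ULN, and leave Part B unchanged.

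No new test is needed. The chemistry panel and weight are already collected at screening (flow chart, section 6.1), and age and sex are known. The planned 40 patients per part stay the same. The cost is that a few low-clearance patients become ineligible for Part A, possibly including some with little chemotherapy left after induction.
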